7.3 Prior and Concomitant Medications

The frequency and percentage of subjects who took at least one dose of medication other than study drug (ABT-414/TMZ/lomustine) during the course of the trial will be summarized by the generic name coded by the World Health Organization (WHO) dictionary. Prior and concomitant medications will be summarized separately.

For each concomitant medication, a listing with subject ID numbers will be provided.

Subjects reporting the same medication generic name two or more times will be counted only once for that generic name. Subjects reporting more than one medication will be counted only once in the total number of subjects taking a concomitant medication.

A similar summary will be prepared for prior medications. In addition, the frequency and percentage of subjects taking 0, 1, 2, 3 and > 3 prior medications will be presented for each treatment arm and overall.

There will be no statistical comparison for the prior and concomitant medications between treatment arms.

7.4 Prior Anti-Cancer Treatment and Surgery

The frequency and percentage of subjects who had prior anti-cancer treatments, including prior radiation therapy and prior cancer medications, will be summarized by treatment name. Radiation therapy will be counted as one anti-cancer treatment. Prior anti-cancer

medications will be summarized using the WHO generic drug name dictionary. A subject who reported two or more uses of the same medication will be counted only once in the total for the associated WHO generic drug name. Subjects will be summarized by the number of prior anti-cancer treatments received (0, 1, 2, 3, and > 3). In addition, reason to stop and the best response to each treatment prior to study drug administration will be summarized.

The frequency and percentage of subjects who had prior brain cancer surgeries will be summarized by the number of prior brain cancer surgeries (0, 1, 2, 3, and 4). In addition, for each of initial, second, third, and fourth brain cancer surgery, extent of procedure will also be summarized.

There will be no statistical comparison for prior anti-cancer treatment/surgery between treatment arms.

8.0 Subject Disposition

Subject disposition summary (number and percentage of subjects) will be presented on all subjects who are registered, as described in Section 13.1 of the study protocol. The number of subjects will be summarized by investigator site and overall.

- Subjects who were registered
- Subjects who screen failed
- Subjects who were randomized
- Subjects who took at least 1 dose of study drug (ABT-414/TMZ/lomustine)
- Subjects who discontinued the study drug

Listing for screen failure reasons/ineligibility will be provided.

In addition, a subject disposition summary will be presented on the ITT population by treatment arm assigned at randomization – the numbers and percentages of subjects who were randomized, took at least 1 dose of study drug, and discontinued the study drug.

Major reason for study drug discontinuation will be summarized by each of ABT-414, TMZ, and lomustine within treatment arm.

No statistical tests will be performed.

9.0 Study Drug Exposure and Compliance

9.1 Dosage

Analyses for the study drug (ABT-414/TMZ/lomustine) treatment will be performed on the Safety population. Longitudinal summary statistics for average dose administered during the study will be presented. The number and percentage of subjects at each treated dose will be presented longitudinally.

An overview of dose modification will be presented by treatment arm, consisting of the number and percentage of subjects who had at least one dose modification for each of ABT-414/TMZ/lomustine throughout the study.

Dose modification of ABT-414/TMZ/lomustine will be summarized for each course/cycle. The frequency and percentage of subjects will be summarized by treatment arm, and reasons for dose modification will also be summarized.

For dose intensity and relative dose intensity of ABT-414 (Arms 1 and 2 only), the following calculation rules are applied:

- The dose intensity of ABT-414 is calculated on actual treatment duration (in weeks) and actual treatment dose received (total dose received in mg/kg). Whenever the treatment is given in cycles and the last planned day of treatment is not the last day of the cycle, the total duration of the treatment must account for this by adding the appropriate number of days to complete the last cycle. That is, if ABT-414 stopped on Day X of a 28-day cycle, the total treatment duration in days is [date of last injection] – [date of first injection] + 1 + (28-X).

- The dose intensity (mg/kg/week) of ABT-414 is the ratio of the total dose received (mg/kg, adjusted by weight) to the total treatment duration (weeks).

$$DI_{observed} (mg / kg / week) = \frac{Total\ dose\ (mg / kg)}{Actual\ total\ treatment\ duration\ (weeks)}$$

- The relative dose intensity is calculated as the ratio of the dose intensity as calculated above to the dose intensity indicated in the protocol, expressed in percent (%). To obtain a correct ratio, the theoretical dose intensity will be expressed in the same units of dose and treatment duration as those used for the actual dose intensity.

$$DI_{protocol} (mg / kg / week) = \frac{Dose\ per\ cycle\ (mg / kg)}{Theoretical\ duration\ of\ one\ cycle\ (weeks)}$$

- The relative dose intensity is usually presented using median and ranges, and by a distribution into categories (relative dose intensity $\leq 70\%$, $> 70 - 90\%$, $> 90 - 110\%$, $> 110 - 120\%$, $> 120\%$).

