5.2 Initial dose and administration

5.2.1 ABT-414

ABT-414 will be given at dose level of 1.0 mg/kg by IV infusion over 30 to 40 minutes once every 2 weeks. The dose of ABT-414 does not have to be adjusted unless there has been at least a 10% change in body weight; recalculation of ABT-414 dose for < 10% weight changes is allowed at the discretion of the Investigator. Each configuration of ABT-414 drug product (Type A and/or Type L) that a subject receives during the study will be recorded.

Subjects will be closely monitored for treatment-related adverse events, especially allergic reactions, during the infusion. For the initial ABT-414 infusion, pre-infusion vital signs should be taken, direct observation is required for the first 15 minutes of the infusion, and subjects should be monitored for 1 hour post-infusion. For subsequent infusions, direct observation and monitoring post-infusion are not required; however, pre-infusion vital signs should still be taken.

Due to the risk of eye toxicity, each administration of ABT-414 should be given with steroid ophthalmic solution. The recommended type, dose, and schedule of eye drops is as follows: dexamethasone 0.1% solution (or equivalent corticosteroid solution), 2 drops (GTTS) in each eye (OU) every 8 hours to start 48 hours prior to ABT-414 dosing and continue for a total of 7 days (or 21 doses total). The type of ophthalmic solution used may vary depending on the availability of the solution at each location. A modification to the eye drop dosing or schedule based on ongoing clinical experience may be suggested.

Allergic reactions of any grade require interruption of ABT-414 treatment and management as described in section [5.5.1.1](#).

Subjects will not be treated at doses less than 0.5 mg/kg. If a subject requires a dose modification below 0.5 mg/kg, the subject will be discontinued from the study treatment.

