5.5.1 ABT-414

ABT-414 will be given by IV infusion over 30 to 40 minutes, on Days 1 (± 2 days) and 15 (± 2 days) of every 28-day cycle. Information about the ABT-414 formulation to be used in this study are presented below:

ABT-414 ^a	
Dosage Form	Lyophilized powder for reconstitution and intravenous admixture
Formulation	Vial
Strength (mg)	20 or 100

a. Information applicable to both ABT-414 and ABT-414 manufactured under two separate manufacturing processes (A and L).

Based upon results from the first clinical and preclinical safety pharmacology evaluation of ABT-414, experience with other inhibitors of EGFR, and experience with MMAF ADCs, potential toxicities may include fatigue, vomiting, thrombocytopenia, allergic reactions, rash, eye complaints, and liver function test abnormalities.

For all observed toxicities, except those listed below, subjects should be assessed for inter-current illness or other causes and treated as appropriate. For severe toxicities (Grade 3 or higher), dosing should be withheld until toxicity resolves to Grade 1 or less (unless otherwise indicated). Dose reduction of ABT-414 for Grade 3 toxicity will be at the discretion of the investigator and the study team. Re-initiation of ABT-414 may be considered at a reduced dose (to 1.0 mg/kg, 0.75 mg/kg, or 0.5 mg/kg) for grade 4 toxicities provided full recovery to grade 1 or less has occurred (unless otherwise indicated).

All dose reductions are permanent, except as listed below (hepatic laboratory abnormalities, section 5.5.1.4).

ABT-414 Dose Modification Table

Toxicity	Starting Dose	First Occurrence	Second Occurrence	Third Occurrence
Grade 1 or 2	1.0 mg/kg	No requirement for dose reduction	No requirement for dose reduction	No requirement for ABT-414 discontinuation
Grade 3	1.0 mg/kg	Can continue at 1.0 mg/kg or reduce to 0.75 mg/kg once the toxicity has resolved to grade 1 or baseline	Can continue at 0.75 mg/kg or reduce to 0.5 mg/kg once the toxicity has resolved to grade 1 or baseline	Can continue at 0.5 mg/kg once the toxicity has resolved to grade 1 or baseline or permanently stop ABT-414
Grade 4	1.0 mg/kg	Reinitiate treatment at 0.75 mg/kg once the toxicity has resolved to grade 1 or baseline	Reinitiate treatment at 0.5 mg/kg, once the toxicity has resolved to grade 1 or baseline	Permanently stop ABT-414

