7.1.1.3 Schedule of disease evaluation

The initial assessment of disease (including measurement of all target lesions) must be performed in the two weeks preceding randomization. Follow-up assessments will be performed every 8 weeks (or earlier if clinically indicated) until disease progression.

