8.3 Interim futility analyses

At interim analysis one or both of the ABT-414 arms might be discontinued based on lack of efficacy for PFS (Reject H1 in favor of H0) according to RANO criteria assessed by IRC.

It is assumed that median PFS is 2.6 months in the control arm and 4.8 months in the treatment arms corresponding to HR equal to 0.54. Assuming an accrual rate of 10 patients/month and activation phase of one year, at least 45 PFS events should be observed. Analyses will be performed when at least 31 PFS events are observed in each comparison. Treatment arms which did not show a minimum level of efficacy, defined as a computed treatment PFS HR lower than 0.91 will be discontinued. The trial will continue with remaining treatment arm(s) and control. There will be no interruption of accrual for the interim analysis.

Treatment PFS HR will be presented with two-sided 95% CI. However, since efficacy data will be analyzed for futility purpose, an alpha spending of 0.00001 will be allocated to the futility analysis. For the final analyses, efficacy endpoint will be tested at a nominal 1-sided alpha level of 0.02499.

For each of the two treatment arms the probability of stopping for futility at the interim is 7.4% if the true PFS HR is 0.54 and 60% if the true PFS HR is 1.0 (no benefit).

Based on the assumed accrual rates and treatment effects stated above, the interim futility analysis is expected to be performed when 90 randomized patients (30 patients per arm) have completed approximately 4 months of follow-up.

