- Any treatment-emergent adverse event leading to dose reduction of lomustine
- Any treatment-emergent adverse event leading to interruption of ABT-414
- Any treatment-emergent adverse event leading to interruption of TMZ
- Any treatment-emergent adverse event leading to interruption of lomustine
- Any treatment-emergent adverse event of special interest
- Any treatment-emergent adverse event leading to death

The treatment-emergent adverse events of special interest will be based on microcystic keratopathy CMQ 80000152 (Section 11.2.1).

Additionally, selected analyses of adverse events will be performed for the subset of subjects with EGFRvIII mutation (on an as-treated basis in the Ev3M population) for the following categories.

- Any treatment-emergent adverse event (descending frequency)
- Any treatment-emergent serious adverse event
- Any treatment-emergent adverse event of special interest

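### SAP 9.1 runs ABT-414 duration to Day 28 of the last cycle although infusions are 14 days apart, so full, on-time dosing scores 50-90% relative dose intensity if the last infusion is Day 1 of cycles 1-5, and always 100% if it is Day 15

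*SAP*

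**What the plan says.** SAP 9.1 (Dosage) divides the total ABT-414 dose in mg/kg by the treatment duration in weeks, and divides that by the protocol intensity (dose per cycle over cycle length) to obtain RDI. RDI is reported by median and range and in five classes: ≤70%, >70-90%, >90-110%, >110-120% and >120%. Days are added to the duration when "the last planned day of treatment is not the last day of the cycle". The formula given is that "the total treatment duration in days is [date of last injection] – [date of first injection] + 1 + (28-X"), where X is the day of the 28-day cycle on which ABT-414 stopped.

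Protocol 5.2.1 gives ABT-414 at 1.0 mg/kg "by IV infusion over 30 to 40 minutes once every 2 weeks", and Protocol 5.5.1 places the infusions "on Days 1 (± 2 days) and 15 (± 2 days) of every 28-day cycle". SAP 9.2 treats one ABT-414 course as 2 weeks. No section adjusts RDI for a patient who stops after a Day 1 infusion.

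**The concern.** The last planned infusion day of a cycle is Day 15, and completing the cycle from there adds 13 days, close to one dosing interval. The formula, however, counts from whichever infusion happened to be last. After a Day 1 infusion it adds 27 days, which charges the patient for a second infusion that was not given, whatever the reason.

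Two patients with no reduction and no delay then differ in RDI only by the half of the cycle in which they stopped. In the class table, the one who stopped after Day 1 looks the same as a patient with a real reduction or delay. The rule is also one-sided: a patient who never resumes after a Day 15 infusion still scores 100%.

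**Working it through.** The documents state no RDI figure to reproduce, so the SAP formula is applied directly.

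**Inputs**
- Dose 1.0 mg/kg every 2 weeks (Protocol 5.2.1), on Days 1 and 15 of a 28-day cycle (Protocol 5.5.1).
- Protocol intensity (SAP 9.1): 2.0 mg/kg ÷ 4 weeks = 0.5 mg/kg/week.
- Full, on-time dosing and constant weight are assumed.

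**Current rule, last infusion in cycle c**
- Day 15: 2c infusions. Duration = 28(c−1) + 14 + 1 + 13 = 28c days. RDI = [2c/(4c)] ÷ 0.5 = 100%.
- Day 1: 2c−1 infusions. Duration = 28(c−1) + 1 + 27 = 28c days. RDI = [(2c−1)/(4c)] ÷ 0.5 = (2c−1)/(2c).

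| Last infusion | Infusions | SAP duration (days) | SAP RDI | SAP class | Last − first + 14 (days) | RDI |
|---|---|---|---|---|---|---|
| Cycle 1 Day 1 | 1 | 28 | 50.0% | ≤70% | 14 | 100% |
| Cycle 2 Day 1 | 3 | 56 | 75.0% | >70-90% | 42 | 100% |
| Cycle 3 Day 1 | 5 | 84 | 83.3% | >70-90% | 70 | 100% |
| Cycle 4 Day 1 | 7 | 112 | 87.5% | >70-90% | 98 | 100% |
| Cycle 5 Day 1 | 9 | 140 | 90.0% | >70-90% | 126 | 100% |
| Cycle 6 Day 1 | 11 | 168 | 91.7% | >90-110% | 154 | 100% |
| Cycle 7 Day 1 | 13 | 196 | 92.9% | >90-110% | 182 | 100% |
| Day 15, cycle c | 2c | 28c | 100% | >90-110% | 28c | 100% |

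**A delayed last infusion.** Suppose the second infusion of cycle 1 is given on Day 22 and is the last.
- Current rule: 21 + 1 + 6 = 28 days, RDI 100%.
- Last − first + 14: 21 + 14 = 35 days (5 weeks), RDI = (2/5) ÷ 0.5 = 80%.

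**The ±2-day window.** A last infusion on Day 13 or Day 17 of cycle 1 gives 26 or 30 days under last − first + 14, so RDI is 107.7% or 93.3%. Both stay in >90-110%. The current rule gives 100% for both.

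**Share of fully dosed patients in the wrong class.** These have an odd number of infusions, at most 9. The stopping-time distribution is not given, so this part rests on assumptions. If stopping is exponential with median m months, the chance of remaining on treatment over one 14-day interval is s = 0.5^(14/(30.4375m)), and the share is (1−s)(1+s²+s⁴+s⁶+s⁸) = (1−s¹⁰)/(1+s).
- Protocol 8.3 states: "It is assumed that median PFS is 2.6 months in the control arm and 4.8 months in the treatment arms".
- m = 4.8: s = 0.9357, share about 25%.
- m = 2.6: s = 0.8846, share about 37%.
- Stops clustered at the scans: Protocol 7.1.1.3 says "Follow-up assessments will be performed every 8 weeks (or earlier if clinically indicated) until disease progression". If each scan is read before the next Day 1 infusion, patients stop after 4, 8 or 12 infusions and the share is 0%. Protocol 6.3.6 allows ±7 days for the scan. A patient who stops just after the cycle 3 Day 1 infusion has 5 infusions and scores 83.3%.

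**The case against.** The strongest reply is that this is a chosen convention. SAP 9.1 openly aims to close out the last cycle, and its denominator is also per cycle. On that reading, a patient given one of two planned infusions received half of that cycle's dose, and 50% is the intended answer. Some Day 1 stops will be toxicity holds, for which a lower RDI is arguably wanted. With last − first + 14, every patient with a single full-dose infusion scores 100%, including one stopped for toxicity before Day 15.

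Part of this stands. The replacement does give up the charge for a withheld, never-resumed Day 15 dose (cycle 1: 50% under the current rule, 100% under the new one). But the current rule does not measure withheld doses consistently. It misses the same event when the withheld dose is the next Day 1 dose (100% under both rules), scores the delayed last infusion above at 100%, and cannot separate a withheld dose from a stop before Day 15 was due.

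Three limits also stand. The 2.6-month median belongs to the control arm, so the 37% applies to an ABT-414 arm only if there is no PFS benefit. Both exponential shares equate stopping treatment with PFS. And because the total dose is adjusted by weight while Protocol 5.2.1 does not require a new dose calculation for weight changes under 10%, observed values will scatter around those in the table, including around the 90.0% boundary.

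**Conclusion.** The concern holds. The formula is at odds with the 14-day schedule and with the 2-week course in SAP 9.2. With full, on-time dosing it understates RDI by 50 percentage points for a last infusion on Day 1 of cycle 1, and by 10 points in cycle 5. It gives the wrong class through cycle 5, and from cycle 6 the right class but too low a value. The share of fully dosed patients affected is not determined by the documents: 0% to about 37%, depending on the assumed stopping pattern.

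The consequence is confined to a descriptive exposure summary in Arms 1 and 2. No test, significance level or sample size depends on it, and real reductions and delays also appear in the dose-modification, schedule-change and adverse-event tables. It should still be corrected, because the class table is a pre-specified output and cannot be read correctly on its own.

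**What to change.** In SAP 9.1, define total ABT-414 duration in days as [date of last infusion] − [date of first infusion] + 14. Leave the protocol intensity at 0.5 mg/kg/week.

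Add a note that RDI does not count a final dose that was withheld and never resumed. The note should direct the reader to two existing summaries. SAP 8.0 states: "Major reason for study drug discontinuation will be summarized by each of ABT-414, TMZ, and lomustine within treatment arm". SAP 11.2 tabulates adverse events leading to ABT-414 discontinuation and includes the category "Any treatment-emergent adverse event leading to interruption of ABT-414".

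The cost is one formula and one note, with no new data. The new formula also no longer needs X, which is hard to define in Arm 1 if ABT-414 and the TMZ cycle fall out of step. The price is the lost charge for a withheld, never-resumed Day 15 dose, which the note discloses.

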9.2 Study Drug Exposure

Analyses for the study drug (ABT-414/TMZ/lomustine) exposure will be performed on the Safety population.

Duration of ABT-414 exposure is defined as total number of weeks a subject received ABT-414, i.e., (last dose date – first dose date + 1)/7. The same calculation applies to TMZ and lomustine.

Descriptive statistics will be presented for the duration of exposure of ABT-414/TMZ/lomustine by treatment arm. The distribution of subjects within the following categories will be summarized: ≤ 4 weeks, > 4 to ≤ 8 weeks, > 8 to ≤ 12 weeks, etc. of ABT-414/TMZ/lomustine, respectively.

An overview of dosing schedule change will be presented by treatment arm, consisting of the number and percentage of subjects who had at least one change in dosing schedule for each of ABT-414/TMZ/lomustine throughout the study. The number and percentage of

subjects at each study drug dose in each treatment course (ABT-414 every 2 weeks; TMZ every 4 weeks; lomustine every 6 weeks) will also be presented.

Dosing schedule change (shortening or delay) of 3 or more days for any of the study drugs (ABT-414/TMZ/lomustine) will be summarized for each course. The frequency and percentage of subjects with no change, delayed, and earlier than per protocol will be summarized respectively, by treatment arm, and reasons for schedule change per course will also be summarized.

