4.2 Design Diagram

This is a comparative randomized, open label, multicenter, multi-arm, Phase II study. The study will consist of three treatment arms; Arm 1 (ABT-414 plus TMZ), Arm 2 (ABT-414 monotherapy), and Arm 3 (mixed control arm of lomustine or TMZ). Subjects will be randomized in a 1:1:1 ratio at the EORTC headquarters after verification of the eligibility criteria discussed in Section 3 of the study protocol.

Arm 1: Subjects will be treated with ABT-414 1.0 mg/kg IV infusion over 30 to 40 minutes once every 2 weeks in combination with TMZ 150 mg/m² Day 1 to 5, for the first 28-day cycle, with dose escalation to 200 mg/m² in subsequent cycles in case of adequate tolerance and until one of the treatment withdrawal criteria has been met. In this Arm 1 the schedule of clinical and lab assessments follows the cycle of TMZ (a delay of TMZ delays the assessment schedule, withholding ABT-414 does not affect the assessment schedule).

Arm 2: Subjects will be treated with ABT-414 monotherapy 1.0 mg/kg IV infusion over 30 to 40 minutes once every 2 weeks until one of the treatment withdrawal criteria has been met.

Subjects in the control arm (Arm 3) will be treated according to the timing of relapse.

Arm 3A: Subjects relapsing during TMZ treatment or within the first 16 weeks after the first day of the last TMZ cycle will be treated with lomustine 110 mg/m² on Day 1 of every 42-day treatment period. Treatment will continue until one of the treatment withdrawal criteria has been met. Lomustine will be given for a maximum of 1 year.

Arm 3B: Subjects relapsing 16 weeks or more after the first day of the last TMZ cycle will be treated with TMZ 150 mg/m² on Day 1 to 5 for the first 28-day cycle, with dose escalation to 200 mg/m² in subsequent cycles in case of adequate tolerance. Treatment will continue until one of the treatment withdrawal criteria has been met.

Treatment should start within 96 hours from randomization. Treatment will be administered until one of the withdrawal criteria described in Section 5.4 of the study protocol has been met. Treatment at further progression will be according to investigators discretion.

Day 1 of the first cycle will be the first day when the study medication is taken.

A schematic of the study design is shown in [Figure 1](#). The study procedures for each visit are outlined in [Table 1](#).

Figure 1. Study Schematic

[figure not shown]

Table 1. Study Activities

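### The SAP's exposure formula leaves out the rest of the last dosing interval, so for equal time on treatment lomustine reads 0 to 4 weeks shorter than ABT-414 (about 2 on average) and TMZ about half a week shorter on average

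*SAP*

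**What the plan says.** SAP 9.2 gives the rule: "Duration of ABT-414 exposure is defined as total number of weeks a subject received ABT-414, i.e., (last dose date – first dose date + 1)/7". The next sentence extends it unchanged to the other two drugs: "The same calculation applies to TMZ and lomustine". Nothing is added for the time between the last dose and the end of the interval it covers. Results are summarised per drug by treatment arm and in bands of "≤ 4 weeks, > 4 to ≤ 8 weeks, > 8 to ≤ 12 weeks, etc".

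The same section lists the course lengths: "ABT-414 every 2 weeks; TMZ every 4 weeks; lomustine every 6 weeks". SAP 4.2 gives the dosing days. Lomustine is given "on Day 1 of every 42-day treatment period"; TMZ in Arm 3B is given "on Day 1 to 5 for the first 28-day cycle", with the same five-day pattern in later cycles.

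SAP 9.1 handles duration differently. For the dose intensity of ABT-414, in Arms 1 and 2 only, dosing that ends before its cycle is over triggers a completion rule: "the total duration of the treatment must account for this by adding the appropriate number of days to complete the last cycle". TMZ and lomustine receive no such completion anywhere in the SAP.

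**The concern.** The SAP describes the quantity as the number of weeks a subject received the drug. For a drug given once every six weeks, the interval from first to last dose is a poor measure of that: a patient with one lomustine dose and a full six weeks of follow-on coverage is recorded as exposed for one day. Because the omitted time grows with the dosing interval, the shortfall differs by drug and so by arm.

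Safety results in SAP 11.1 and 11.2 are counts and percentages of subjects, without exposure adjustment or formal comparison. A reader will set those frequencies beside duration of exposure. If ABT-414 appears to have been given for longer than lomustine when the time on treatment was the same, tolerability and exposure are misread.

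**Working it through.** The SAP states no numerical exposure figure, so there is nothing to reproduce. The check applies its formula to on-schedule dosing.

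**Inputs.** Formula, course lengths and bands: SAP 9.2. Dosing days: SAP 4.2. Assumed median PFS of 2.6 months (control) and 4.8 months (treatment), used only as illustrative stop times: SAP 4.4. A 60/40 lomustine/TMZ split of the control arm is an assumption taken from the historical relapse timing in Protocol 1.2.

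**Days omitted at the end of a complete interval.**
- ABT-414: 14 − 1 = 13
- TMZ: 28 − 5 = 23 (last dose on day 5)
- Lomustine: 42 − 1 = 41

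**Reported weeks for equal time on treatment.** At 12 weeks the last dosing days are 71 (ABT-414), 61 (TMZ) and 43 (lomustine), giving 71/7 = 10.14, 61/7 = 8.71 and 43/7 = 6.14. Other stop times work the same way:

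| Weeks on treatment | ABT-414 | TMZ | Lomustine | ABT-414 − lomustine | ABT-414 − TMZ |
|---|---|---|---|---|---|
| 6 | 4.14 | 4.71 | 0.14 | 4.00 | −0.57 |
| 8 | 6.14 | 4.71 | 6.14 | 0.00 | 1.43 |
| 12 | 10.14 | 8.71 | 6.14 | 4.00 | 1.43 |
| 16 | 14.14 | 12.71 | 12.14 | 2.00 | 1.43 |
| 24 | 22.14 | 20.71 | 18.14 | 4.00 | 1.43 |

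Stopping at the assumed control median PFS (day 79) gives the 12-week row.

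**Average gap.** Within each 42-day period the last ABT-414 dose falls on day 1, 15 or 29 and the lomustine dose on day 1. The gap is therefore 0, 2 or 4 weeks, each for a third of stop times, with mean 2 weeks. Averaged over evenly spread stop times, the omitted days are 6.5 (ABT-414), 9.9 (TMZ) and 20.5 (lomustine). The differences from ABT-414 are 20.5 − 6.5 = 14 days for lomustine and 9.9 − 6.5 = 3.4 days for TMZ.

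**Identical exponential stop times (400,000 draws).**
- Median 2.6 months, true mean 16.3 weeks: reported means are 15.4 (ABT-414), 15.0 (TMZ) and 13.6 (lomustine). A 60/40 control mix gives 14.2, about 1.3 weeks below ABT-414. Reported medians are 10.1, 8.7 and 6.1 weeks against a true 11.3.
- Median 4.8 months: reported means are 29.2, 28.7 and 27.3; reported medians are 20.1, 20.7 and 18.1.

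**Bands.** On-schedule lomustine can read only 0.14, 6.14, 12.14, 18.14 weeks and so on. One completed course lands in the lowest band, and the band above 8 and up to 12 weeks is empty unless a dose is delayed.

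**SAP 9.1 against 9.2.** Six on-time ABT-414 infusions end on day 71, which is day 15 of cycle 3. The 9.1 rule gives (71 + 28 − 15)/7 = 12.0 weeks; the 9.2 rule gives 10.14.

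**Completing the interval.** With f the first day of the last dose or cycle, (f − 1 + interval)/7 at 12 weeks gives (71 − 1 + 14)/7, (57 − 1 + 28)/7 and (43 − 1 + 42)/7, each 12.0.

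**Why truncation is needed.** If treatment stops at the week-8 MRI, the last ABT-414 and lomustine doses are both on day 43. Completion without truncation gives 56/7 = 8 weeks for ABT-414 and 84/7 = 12 for lomustine. In the 2.6-month simulation it adds 13/7 and 41/7 weeks to the means: 15.42 + 1.86 = 17.3 and 13.58 + 5.86 = 19.4, against a true 16.3. Truncated at the stop date, every drug returns about 16.3.

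**The case against.** The strongest defence is that a first-to-last-dose interval is a legitimate quantity and matches how adverse events are counted. SAP 11.1 takes treatment-emergent events up to 35 days after the last dose, so that window follows the last dose, not the cycle end. In the 12-week example the window closes on day 71 + 35 = 106 for ABT-414 and day 43 + 35 = 78 for lomustine. That four-week difference in event capture is real, and a table showing 12 weeks for each drug would hide it. This stands, and it is why the first-to-last-dose interval should be kept beside a corrected duration. It does not rescue the present label, which claims to be weeks of receiving the drug.

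A reader might infer several stronger things that the documents do not support:
- **That ABT-414 is overstated by 65% against control.** The ratio 10.14/6.14 = 1.65 belongs to a 12-week stop and to lomustine alone. At 8 weeks the gap is zero. The gap is bounded in absolute terms, so it matters less for long treatment. Control is lomustine or TMZ, and SAP 9.2 summarises each drug separately.
- **That this table is the only context for adverse event frequencies.** SAP 9.2 also tabulates dose by course, so course counts are visible. SAP 8.0, 9.1 and 11.2 report discontinuation reasons, dose modifications, and events leading to reduction or interruption.
- **That SAP 9.1 flatly contradicts 9.2.** The 9.1 rule serves the denominator of a dose rate for ABT-414. The two can coexist, though they give one patient two durations for the same drug.

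**Conclusion.** The point holds as a flaw in a descriptive derivation, of modest size. The same arithmetic applied to three schedules gives a shortfall that depends on the drug, and on average it makes ABT-414 exposure look longer than lomustine and slightly longer than TMZ. The clearest failure is the lomustine patient with one completed course, reported at 0.14 weeks.

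The sizes assume on-schedule dosing with no delays. The averages also depend on the stop-time distribution, and the control-arm figure of about 1.3 weeks rests on the assumed 60/40 split. SAP 11.1 plans no safety tests or confidence intervals, and no endpoint or decision uses exposure duration. An inference that efficacy conclusions are affected would be wrong.

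**What to change.** In SAP 9.2, define duration for every drug as (first day of last dose or cycle − first dose date + planned interval)/7, with intervals of 14 days for ABT-414, 28 for TMZ and 42 for lomustine. Truncate at the earliest of progression or recorded treatment discontinuation, death, start of further anti-cancer therapy, or data cut-off. Truncation at progression or discontinuation is essential, because without it the bias reverses in favour of lomustine. State that the discontinuation date is the date of the decision to stop; if the last dose date were used instead, truncation would bring back the present formula.

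Use the new duration for the 4-week bands. Beside it, report the number of courses and the first-to-last-dose interval, labelled as such, since the latter determines the treatment-emergent event window.

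The cost is a wording change and one extra derivation. Dosing, progression, death and subsequent-therapy dates are already needed for other planned analyses.
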